10.3.6. Additional Endpoint Analyses

The analyses of the percentage of target aneurysm ruptures up to 1 year, 3 years and 5 years post-procedure and of the percentage of no migration (defined as ≤ 2 mm) of the device at 1 year, 3 years and 5 years post-procedure will be conducted on the PP population using the observed data. Both endpoints are evaluated by the independent core laboratory.

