3.2.4. Additional Endpoints

- The percentage of target aneurysm rupture up to 1 year, 3 years and 5 years. This endpoint will be evaluated by the independent core laboratory.
- No migration (defined as $\leq 2\text{mm}$) of the device at 1 year, 3 years and 5 years. This endpoint will be evaluated by the independent core laboratory.

4. Study Population

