6.2.3. Core Laboratory for Image Evaluation

An independent radiographic core laboratory shall be utilized to provide an unbiased and standardized assessment of all imaging. All subject PHI will be removed before an image is uploaded and evaluated. The core lab assessor will be blinded to subjects' previous medical history. The core lab will evaluate the following:

- Aneurysm and vessel dimensions
- Ability to retain embolic coils without coil protrusion/herniation (yes/no)
- Aneurysm occlusion: evaluated per the Raymond– Roy scale referenced in Section 3.2.2
- Parent and branch vessel stenosis: evaluated on a scale of 0-50% and > 50-100%
- Device migration: migration is defined as > 2mm

All imaging shall be performed in accordance to the core laboratory recommended protocol provided to the sites. A copy of the study angiograms will be submitted to the core lab.

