7.8. Follow-up Angiography

Any imaging performed (DSA, MRA, CTA) per standard of care after the study procedure and prior to the final study visit will be collected. **A DSA is required at the 1 year follow-up.** Either DSA or MRA is required at the 3 year and 5 year follow-up visits. The intent is to evaluate aneurysm occlusion and the PulseRider implant. The Investigator will grade aneurysm occlusion according to the Raymond Scale. Should any imaging be considered necessary at a non-study required time point, it is requested that an assessment of the treated aneurysm be performed and the appropriate eCRF including a reason for the unscheduled procedure should be completed. Any imaging performed as standard of care will be collected and sent to the core lab.

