8.5. Clinical Events Committee

The Clinical Events Committee (CEC) will consist of a minimum of three independent physicians with expertise in neurosurgery, neurology or interventional neuroradiology and who are not otherwise involved with the study. The CEC will review all reportable adverse events to adjudicate the safety endpoint, in addition to AEs of interest specified in the CEC charter.

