10.1.6. Analysis Datasets

Modified Intent to Treat Analysis Set

The mITT analysis set consists of all enrolled subjects in whom treatment with the PulseRider device is attempted as defined by advancement of any portion of the PulseRider device outside of the distal end of the microcatheter inside the subject. This includes subjects in which the PulseRider is not fully advanced outside of the microcatheter. It is possible that the PulseRider device may not reach the target aneurysm, and as a result the treating physician does not advance the device outside of the distal end of the microcatheter. In the rare event that this happens, the subject will not be considered part of the mITT population and will instead be followed for 30 days.

Per Protocol (PP) Analysis Set

The PP analysis set consists of all subjects who meet the following criteria:

- there are no major deviations from the protocol eligibility criteria or DAPT requirements
- the subject is successfully implanted with the PulseRider device

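### The target aneurysm rupture endpoint can understate ruptures: it goes to a core lab whose reading list omits rupture, and it is analysed only on per-protocol observed data

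*Combined protocol and SAP*

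**What the plan says.** Section 3.2.4 lists as an additional endpoint "The percentage of target aneurysm rupture up to 1 year, 3 years and 5 years". Sections 3.2.4, 10.1.3 and 10.3.6 all name the independent core laboratory as its evaluator. Section 10.3.6 says that the analyses of rupture and device migration "will be conducted on the PP population using the observed data. Both endpoints are evaluated by the independent core laboratory".

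Four other sections bear on this:

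- **Core lab task (6.2.3).** "The core lab assessor will be blinded to subjects' previous medical history. The core lab will evaluate the following": dimensions, coil retention, occlusion, stenosis and migration. Rupture is not among them.
- **PP set (10.1.6).** It requires no major eligibility or DAPT deviation and that "the subject is successfully implanted with the PulseRider device".
- **Denominators (10.3.1).** Percentages leave out subjects with missing data.
- **CEC (8.5).** "The CEC will review all reportable adverse events to adjudicate the safety endpoint", together with events of interest named in its charter.

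**The concern.** Rupture is a clinical event. Section 1.1 gives reducing the risk of subarachnoid hemorrhage as the main goal of treating an aneurysm, and Table 1.5.1A lists aneurysm perforation or rupture as an anticipated risk. The plan nevertheless measures it as it measures device migration, by an imaging reader and in successfully implanted subjects only.

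Three gaps follow. The reader who is to evaluate rupture is not told to look for it. A rupture during a failed implant attempt falls outside the analysis set by definition, as does one in a subject with a major DAPT deviation. And a subject who dies of a rupture before any imaging has no stated way to be counted. With few events expected, one or two such cases could change the named rupture rate that goes forward with the premarket application.

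**Working it through.** The documents state no rupture rate, power or performance goal, so there is no rupture figure to reproduce. The check follows each kind of rupture through the plan and then bounds the number of subjects affected.

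**1. Where each rupture is counted**

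| Rupture | Rupture percentage (10.3.6) | Elsewhere |
|---|---|---|
| Implanted, no major deviation, imaged | Yes, if the core lab reads for it | mITT adverse event summaries (10.3.7) |
| Implanted, no major deviation, no image | No stated route | Same |
| Failed implant | No | Same |
| Major eligibility or DAPT deviation | No | Same |

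In any row, a rupture causing neurological death or major ipsilateral stroke by 1 year also counts in the primary safety endpoint, which uses mITT (3.2.1, 10.3.4). The summaries listed in 10.3.7 are all adverse events, serious events, unanticipated device effects, deaths, device- and procedure-related events and neurologic events. None is target aneurysm rupture. The sensitivity and subgroup analyses (10.3.10, 10.3.11) cover only the primary endpoints.

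**2. How many failed implants can lie outside PP**

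Inputs: 160 subjects; a technical success goal of 79%; the stated minimum observed rate of 85% (10.1.2). Assume that the device is attempted in all 160. The lower bound is p − 1.96 × √(p(1 − p)/160).

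- 136/160 = 85.0%: lower bound 79.5%, above 79%.
- 135/160 = 84.4%: lower bound 78.7%, below 79%.

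This reproduces the plan's 85%. Technical success can therefore be met with up to 160 − 136 = 24 failed implants. At the other end, the earlier HDE study reported 34/34 successes (1.3.2), which would mean none. The range is 0 to 24. Deviations add to it, but the documents give no number for them.

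**3. Effect on the percentage (assumed rupture counts, for illustration; Clopper-Pearson 95% intervals)**

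| Implanted / failed | Ruptures, implanted / failed | PP | mITT |
|---|---|---|---|
| 160 / 0 | 1 / 0 | 1/160 = 0.63% (0.02–3.4) | 1/160 = 0.63% (0.02–3.4) |
| 144 / 16 | 1 / 1 | 1/144 = 0.69% (0.02–3.8) | 2/160 = 1.25% (0.15–4.4) |
| 136 / 24 | 1 / 1 | 1/136 = 0.74% (0.02–4.0) | 2/160 = 1.25% (0.15–4.4) |
| 136 / 24 | 1 / 0 | 1/136 = 0.74% (0.02–4.0) | 1/160 = 0.63% (0.02–3.4) |

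PP is lower than mITT only when failed implants rupture at a higher rate than implanted subjects. In the last row PP is slightly higher.

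**4. Effect of an unimaged rupture**

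Take 144 PP subjects with one imaged and one unimaged rupture. The full count is 2/144 = 1.39%. If the unimaged case is treated as missing, the result is 1/143 = 0.70%; if it is treated as no rupture, 1/144 = 0.69%. Either way the percentage is too low.

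**The case against.** The strongest reply is that the trial does not lose these events. Every neurological event and every serious event is reportable (8.1.1), the CEC reviews all of them, and the data monitoring committee assesses them (8.6). Serious events, deaths and neurologic events are summarised on mITT. Subarachnoid hemorrhage is within the stroke definition, and Section 10.3.4 counts qualifying events from a failed attempt as failures on the primary safety endpoint. A reader might infer that fatal ruptures and those in failed implants would go unseen. The documents do not support that; what can be missing is their place in one descriptive percentage.

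The imaging route is also wider than the reading list suggests. Section 7.8 says: "Any imaging performed (DSA, MRA, CTA) per standard of care after the study procedure and prior to the final study visit will be collected", and sends that imaging to the core lab. Section 7.6 asks for MRI or CT at a suspected stroke, and nothing says that those images are withheld from the core lab. Blinding to previous history does not stop a reader from seeing hemorrhage. The clear imaging gap is the rupture with no image at all.

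Three further points stand. A low bias from the PP set is plausible, since an attempt can itself cause rupture, but it is not shown. PP is a defensible set for the late durability of an implant and matches most secondary endpoints (10.3.5). The CEC charter, which is not part of the document, may already name rupture.

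None of this supplies a named rupture count on mITT. The safety composite omits a rupture that stays below its stroke definition or occurs after 1 year, and the adverse event categories do not attribute a hemorrhage to the target aneurysm.

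**Conclusion.** The concern holds for the rupture endpoint, not for safety reporting as a whole. Three things follow directly from the text: rupture is assigned to a core lab whose reading list omits it; ruptures in failed implants or in subjects with major deviations are outside the percentage; and an unimaged rupture has no counting rule.

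The size is modest and uncertain. Failed implants remove between 0 and 24 of 160 subjects, assuming that all 160 are attempted and technical success is met; 24 is a ceiling, not an expectation. The loss through deviations is unstated. In the illustration with one rupture in each group, the percentage is 0.69% to 0.74% on PP against 1.25% on mITT. With no rupture among failed implants, the implant criterion loses no event.

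This is an additional endpoint with no hypothesis test, so study success and power do not change. It still merits correction, because it is the only output that names the outcome treatment is meant to prevent.

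**What to change.** - In Sections 3.2.4, 10.1.3 and 10.3.6, have the CEC adjudicate target aneurysm rupture from the reportable adverse events it already reviews, with any imaging as support. Add rupture to the CEC charter if it is not there.
- State that a clinically reported rupture without images is counted when the CEC confirms it.
- Report the 1-year rate on mITT, with PP as supporting.
- Report the 3- and 5-year rates on PP or on implanted subjects, and say why: Section 10.3.4 follows failed implants only up to 1 year, so an mITT rate would not be complete at those times.
- Leave device migration with the core lab.

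The cost is wording in three sections, possibly a charter line, a small amount of extra adjudication and one extra table. It needs no new visit or imaging.

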10.3.7. Safety Analyses

AE summaries (number of events and incidence) conducted on the mITT analysis set will be presented for:

- All AEs
- SAEs
- UADEs
- Deaths
- Device and Procedure Related AEs
- Neurologic AEs

Study device malfunctions observed intra-operatively and overtime thereafter will be summarized using the mITT analysis set.

AE and study device malfunction summaries will also be provided in the same fashion as above for T and Y shape devices separately.

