5.1.8. Duration of Implant Exposure

The PulseRider is a permanent implant. In the event the PulseRider device needs to be removed during the course of a procedure for any reason, i.e. wrong size or shape, device malfunction or device failure, the PulseRider shall be returned to Pulsar Vascular, Inc. per standard institutional practices for biohazard waste. Please refer to Section 5.1.10 regarding complaint handling.

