10.1.4. Adverse Events and Clinical Complications

Adverse Events, SAEs, device- or procedure-related AEs, USADEs, UADEs, and deaths will be coded using the MedDRA system and summarized with frequencies.

Study device malfunctions will also be summarized.

In addition, a listing of adverse events will be provided for any subject that was consented and started the study procedure but did not undergo attempted treatment with the study device and therefore is not part of the modified Intent To Treat (mITT) population.

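### The malfunction summary is run on mITT, which excludes a subject whose only device failed inside the microcatheter, and no planned output names that malfunction

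*Combined protocol and SAP*

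**What the plan says.** Section 10.3.7 fixes the population for the malfunction table: "Study device malfunctions observed intra-operatively and overtime thereafter will be summarized using the mITT analysis set". The by-shape tables follow the same rule: "AE and study device malfunction summaries will also be provided in the same fashion as above for T and Y shape devices separately".

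Section 10.1.6 makes mITT membership depend on treatment having been "attempted as defined by advancement of any portion of the PulseRider device outside of the distal end of the microcatheter inside the subject". Partial advancement is enough: "This includes subjects in which the PulseRider is not fully advanced outside of the microcatheter". The section then describes the opposite case: "It is possible that the PulseRider device may not reach the target aneurysm, and as a result the treating physician does not advance the device" out of the catheter. There, "the subject will not be considered part of the mITT population and will instead be followed for 30 days". The protocol describes this as rare and attaches no figure to it.

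Section 10.1.4 says that malfunctions will be summarized, without naming an analysis set. For subjects outside mITT it adds one output: "a listing of adverse events will be provided for any subject that was consented and started the study procedure" without attempted device treatment. That output is confined to adverse events.

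Capture is wider than analysis. Section 7.4 makes device malfunction a procedural assessment, and Section 8.1.7 requires every study device deficiency to be entered in the eCRF.

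**The concern.** Whether a subject is in the table can depend on the event the table counts. Under Section 8.1.7 a malfunction is a failure to perform as intended, whether or not the device has left the microcatheter. Table 1.5.1A lists delivery failure and fracture of the delivery wire among the anticipated risks. If such a failure happens before any part of the only device used has come out, the subject is already enrolled (Section 7.2.1) but is not in mITT. The malfunction is then recorded but not tabulated, and if no adverse event accompanies it, the Section 10.1.4 listing does not show it either.

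Technical success does not fill the gap. Its definition requires access to the aneurysm and successful detachment, so this event would be a failure, but Section 10.3.5 analyzes it on mITT as well.

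At stake is the descriptive malfunction rate in a study that Section 2.1 says will support a premarket approval application.

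**Working it through.** The documents state no malfunction rate, so there is no plan figure to reproduce. The check has two parts.

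**Tracing the rules**

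| Event in an enrolled subject | In mITT (10.1.6)? | In malfunction summary (10.3.7)? | In non-mITT listing (10.1.4)? |
|---|---|---|---|
| Device partly advanced, then fails | Yes | Yes | Not applicable |
| Device deployed, detachment fails | Yes | Yes | Not applicable |
| First device jams in catheter, another is advanced | Yes | Can be counted | Not applicable |
| Only device fails inside the catheter | No | No | Only an accompanying adverse event |
| Sound device cannot reach the aneurysm (anatomy) | No | No malfunction to count | Only an accompanying adverse event |

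Only the fourth row is lost.

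**Size**

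Inputs: n = 160 planned enrolment (Protocol Summary). The rest are assumptions:
- k = subjects whose only device malfunctioned inside the catheter
- m = subjects with any other malfunction
- device use was begun in all n subjects

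Formulas:
- planned rate = m/(n − k)
- rate over all subjects in whom use was begun = (m + k)/n
- difference = k(n − m − k) / [n(n − k)], which is positive whenever k > 0 and m + k < n

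| m | k | mITT rate | All-begun rate | Difference (points) |
|---|---|---|---|---|
| 2 | 0 | 2/160 = 1.25% | 2/160 = 1.25% | 0 |
| 2 | 1 | 2/159 = 1.26% | 3/160 = 1.88% | 0.62 |
| 2 | 3 | 2/157 = 1.27% | 5/160 = 3.13% | 1.85 |
| 2 | 5 | 2/155 = 1.29% | 7/160 = 4.38% | 3.08 |
| 0 | 3 | 0/157 = 0% | 3/160 = 1.88% | 1.88 |
| 5 | 3 | 5/157 = 3.18% | 8/160 = 5.00% | 1.82 |

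Each omitted subject costs about 0.6 percentage points. For m = 2 and k = 3 the Clopper-Pearson 95% intervals are 0.15% to 4.53% on mITT and 1.02% to 7.14% on all begun. They overlap widely, but the mITT figure is biased as well as imprecise.

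**Exclusions for anatomy**

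Suppose j further subjects have a sound device that never leaves the catheter. The mITT rate becomes m/(n − k − j). With k = 0, m = 2 and j = 3 it is 2/157 = 1.27% against 2/160 = 1.25%, a trivial shift upward. With k = 3, m = 2 and j = 3 it is 2/154 = 1.30% against 5/160 = 3.13%. The planned rate is too low whenever kn > (m + k)(k + j). For k = 1 and m = 2 this is 160 > 3(1 + j), which fails only at j = 53 or more. For any plausible j, the net effect is understatement once k is at least 1.

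**The case against.** The strongest reply is that very little is lost. Partial advancement, failed detachment and later malfunctions stay in mITT, as does a jam followed by a second, advanced device. The protocol calls the exclusion rare and illustrates it with a device that does not reach the aneurysm, which may be anatomy. In the earlier ANSWER study (Section 1.3.2) the device was placed and detached in 34 of 34 cases. The table carries no hypothesis, performance goal or alpha. Section 10 also defers detail to a separate SAP.

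Most of this stands and limits the size. It does not remove the point. Zero failures in 34 gives an exact 95% upper limit of 1 − 0.025^(1/34) = 10.3%, so a low failure rate is not excluded. The choice of mITT is a stated rule, not a detail left open.

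Four stronger readings are tempting, and the documents do not support them.

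- A reader might infer that delivery failures in general drop out. Only those in which no device ever leaves the catheter do.
- A reader might infer that these malfunctions go unrecorded. Sections 7.4 and 8.1.7 require them to be recorded, Section 8.4.1 requires study device malfunctions to be reported to the sponsor, and Section 5.1.10 requires complaint analysis of a suspected malfunction. The disposition tables in Section 10.3.2 should also show enrolled but untreated subjects, though not the reason.
- A reader might infer from Section 5.1.8 that replacement devices are expected, so that the T and Y tables need a per-device denominator. That section covers removal and return and does not mention replacement. Section 10.3.7 states no denominator that would exclude counting devices.
- A reader might infer that the study conclusions are affected. Re-basing this table leaves every primary and secondary test as it is.

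**Conclusion.** The point holds in a narrow form. Under Sections 10.1.6 and 10.3.7 together, a malfunction that stops the only device inside the microcatheter leaves both the numerator and the denominator of the malfunction summary, and the Section 10.1.4 listing does not recover it. When such malfunctions occur, the rule understates the rate. Exclusions for anatomy alone have a negligible effect.

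The size is unknown, because the documents give neither a malfunction rate nor a frequency for the exclusion. If there are none, nothing changes. With one to three among 160, and few other malfunctions, the loss is about 0.6 to 1.9 percentage points. That is small in absolute terms, but at m = 2 and k = 1 the reported rate is only about two-thirds of the full one (1.26/1.88 = 0.67). These figures rest on assumed counts and on device use having been begun in all 160 subjects. The consequence is confined to descriptive device-performance reporting.

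**What to change.** In Section 10.3.7, summarize malfunctions over all enrolled subjects in whom use of a PulseRider was begun, meaning that a device was introduced into the microcatheter. Put the T and Y tables on the same subject base, and keep the mITT table as a supplement. In Section 10.1.4, extend the listing of non-mITT subjects to device malfunctions.

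The cost is a change of wording, one re-based set of tables and one longer listing. The malfunctions themselves are already to be recorded under Sections 7.4 and 8.1.7. One item needs confirming: neither the procedure data in Section 7.4 nor the accountability log items in Section 5.1.9 name introduction into the microcatheter, and the log items do not name device shape. The sponsor should check that the procedure eCRF identifies the new denominator, and add a field if it does not. The listing does not depend on that field and can be extended in any case. The downside is that the reported malfunction rate may be slightly higher.

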10.3.8. Plans for Interim Analyses

There are no planned interim analyses.

10.3.9. Handling of Missing Data

Missing primary safety and effectiveness endpoint data will be imputed as per the multiple imputation method described in section 10.3.4. The secondary effectiveness endpoint is expected to have minimal to no missing data and analysis will not make use of any imputations.

10.3.10. Sensitivity Analyses

As a sensitivity analysis, the primary safety and effectiveness endpoints will be analyzed as described in section 10.5.4 but without imputing missing endpoint data using the Clopper-Pearson method.

Other sensitivity analyses will analyze the primary endpoints as follows:

- Consider all missing endpoints as successes,
- Consider all missing endpoints as failures,
- A Tipping point analysis which attempts to answer how many subjects with missing primary endpoint data need to change to either successes or failures for success on the endpoint to no longer hold.

10.3.11. Sub-Group Analyses

Proportions of subjects and 95% confidence intervals of the primary safety and effectiveness endpoints will be presented for the mITT population set with only the observed data and of the primary effectiveness endpoint for the PP population set with only the observed data as appropriate, in the following subgroups:

- sex. Males and Females will also be statistically compared at the 0.1 alpha level using a chi-square test based on a normal distribution.
- race
- ethnicity
- age category (18-35, 36-50, 51-64, 65-75, and 76-80 years)
- aneurysm location - basilar, carotid terminus, MCA and ACOM

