7.15. Schedule of Assessments Table

This table provides an overview of the procedures to be performed at each study visit and the visit window.

Table 7.15A Schedule of Assessments

Assessments	Pre-procedure* (0-60 days of the procedure)	Immediately Pre-Procedure	Procedure	Immediately Post-procedure	Discharge	30 Day Follow-up (+/- 7 days)	180 Day Follow-up (+/-42 days)	1 Year Follow-up (+/-60 days)	2 Year Telephone Call (+/- 60 days)	3 Year Follow-up (+/-60 days)	4 Year Telephone Call (+/- 60 days)	5 Year Follow-up (+/-60 days)	Unscheduled Visit
Informed Consent	X												
Medical History	X												
Labs (CBC & Blood Coagulation Tests)	X												
Neurological Exam	X				X	X	X	X		X		X	X
NIH Stroke Scale Assessment		X			X	X	X	X		X		X	X
Modified Rankin Scale		X			X	X	X	X	X	X	X	X	
Pregnancy Test		X [*]											
Conventional Catheter Angiography – DSA [§]	**X	***X				O ^β	O ^β	X ^{†\$}	O ^β	X ^{††}	O ^β	X ^{††}	O ^β
MR Angiography [§]						O ^β	O ^β		O ^β	X ^{††}	O ^β	X ^{††}	O ^β
CT Angiography [§]	**X					O ^β	O ^β		O ^β		O ^β		O ^β
Review of Adverse Events			X	X	X	X	X	X	X	X	X	X	X
Review of Medications Taken	X		X	X	X	X	X	X	X	X	X	X	X
Medical Resource HECON		X	X	X	X	X	X	X	X	X	X	X	X

*With the exception of the baseline DSA or CTA and the pregnancy test, all baseline evaluations must be completed within 60 days prior to the index procedure and may occur on the procedure day prior to the procedure.

**Baseline imaging may be either CTA or DSA and must be completed within 180 days prior to the index procedure.

***Three treatment angiograms: 1) Immediately pre-procedure image is before PulseRider implant to confirm eligibility 2) Procedure image immediately after PulseRider placement 3) Immediately post-procedure is after coiling.

^β Any imaging related to the target aneurysm conducted post-procedure and prior to the final study visit, per standard of care, will be collected.

[†] Imaging for 1 year post-procedure must be DSA.

^{††} Imaging for 3 year 5 years post-procedure must be DSA or MRA.

[‡] Pregnancy test must be completed on day of procedure for women of childbearing potential.

[§] Subjects who were not implanted with the PulseRider device are not required to undergo DSA imaging at 1 year.

8. Assessment of Safety

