10.3.4. Primary Endpoint Analyses

Primary Safety Endpoint

The primary safety endpoint analysis will be conducted on the mITT analysis set.

If a subject experienced a death due to neurological causes or a major ipsilateral stroke in downstream territory within a year post-procedure then subject will be deemed a failure on the endpoint. If a subject completed the 1 year follow up and did not experience any such event then subject will be deemed a success on the endpoint. If a subject did not complete the 1 year follow up and did not experience such event then the subject will be imputed with a multiple imputation method that will make use of the similarities between the subject's demographic, procedural, and aneurysm characteristics with those of the subjects with a non-missing endpoint (those who either experienced an event and those who completed the study without experiencing an event). The imputation method will also account for the length of time between the procedure and the last time the subject was seen. The longer that time period is, the less likely the subject will be imputed with an event.

Subjects for whom implantation of the PulseRider was attempted but not successful will be followed up to a year. Any safety events which occur due to attempted implant or from retreatment, and which meet the primary safety endpoint definition will count as failures in the analysis. If such a subject is lost to follow-up then subject will be imputed with data based on other subjects for whom the implantation was not successful but who were not lost to follow-up.

The multiple imputation method results in a large collection of imputed datasets. The proportion of primary endpoint events and its variance is computed for each dataset. Within and between imputation variances are then combined according to Rubin's method [Rubin 1996] in order to produce a single variance estimate for the proportion of events.

The endpoint will be considered successful if the upper bound of the 2-sided 95% normal approximation based confidence interval for the rate of events is less than a performance goal of 15%.

Primary Effectiveness Endpoint

The primary effectiveness endpoint analysis will be conducted on the PP analysis set.

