Success on this endpoint is defined as complete aneurysm occlusion (Raymond I) without retreatment or significant parent artery stenosis (> 50% stenosis) at 1 year post-procedure. If the 1 year imaging is not available and if the subject did not experience a retreatment then the subject will be imputed using an imputation method that will make use of the subject's own past occlusion and stenosis evaluations if available and the similarities between the subject's demographic, procedural, and aneurysm characteristics with those of the subjects with a non-missing endpoint.

The multiple imputation method results in a large collection of imputed datasets. The proportion of complete aneurysm occlusion and its variance is computed for each dataset. Within and between imputation variances are then combined according to Rubin's method in order to produce a single variance estimate for the proportion of complete aneurysm occlusion.

The endpoint will be considered successful if the lower bound of the 2-sided 95% normal approximation based confidence interval for the rate is greater than a performance goal of 46.3%.

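### The mITT occlusion rates by subgroup can lose failed implants, because those subjects need no 1-year DSA and only observed data are used

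*Combined protocol and SAP*

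**What the plan says.** Section 10.1.6 defines the two analysis sets. "The mITT analysis set consists of all enrolled subjects in whom treatment with the PulseRider device is attempted", and attempt is read broadly: "This includes subjects in which the PulseRider is not fully advanced outside of the microcatheter". Failed implants are therefore in mITT once any part of the device has left the microcatheter. The PP set requires that "the subject is successfully implanted with the PulseRider device" and also excludes major eligibility and DAPT deviations.

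Section 10.3.4 places the main test on the narrower set: "The primary effectiveness endpoint analysis will be conducted on the PP analysis set". Section 10.3.11 then shows the same endpoint by subgroup on both sets. For mITT, the safety and "effectiveness endpoints will be presented for the mITT population set with only the observed data". Section 10.3.1 adds that percentages are taken over subjects without missing data.

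The endpoint is core-laboratory Raymond I occlusion at 1 year, without significant parent artery stenosis or prior retreatment (3.2.2). A footnote to the schedule in 7.15, repeated in the Protocol Summary, reads: "Subjects who were not implanted with the PulseRider device are not required to undergo DSA imaging at 1 year". Routine imaging is still collected and sent to the core laboratory if it is done (7.8).

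**The concern.** The subjects who make mITT broader than an implanted-only set are the ones for whom the endpoint image is not required. With observed data only, a failed implant that has no 1-year image and no recorded retreatment has no endpoint and leaves the denominator. The row keeps the mITT label but moves towards the implanted subjects.

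A second route pushes the same way. A failed implant may be treated with another technique and imaged in routine care. If that treatment is not classed as retreatment, a Raymond I grade meets the written endpoint and counts as a success in a summary of this device.

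These rows matter because every other occlusion analysis is on PP (10.3.4, 10.3.5), and because 10.3.11 is the only place where effectiveness is broken down by location. The study adds MCA and ACOM to the territories studied before (1.2). Technical success is analysed on mITT (10.3.5), but no breakdown by location is planned. A higher failure rate in one territory could therefore go unseen in the planned effectiveness tables. The male-female comparison at the 0.1 level uses the same data.

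**Working it through.** **Inputs**
- Expected complete occlusion 58.8% (10.2), taken here as the rate among implanted subjects.
- 160 subjects, technical-success goal 79%, stated pass mark 85% (10.1.2).
- *f* = share of mITT subjects whose implant failed. This is an assumption, as the protocol gives no expected value. The earlier study of the device had 34 of 34 implanted (1.3.2).
- *q* = share of failed implants that enter as observed failures. This is also an assumption.
- For simplicity, implanted subjects are treated as having complete data and mITT as 160 subjects.

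**The plan's own figures.** With 136/160 = 85.0%, the lower 95% limit is 0.850 − 1.96 × √(0.85 × 0.15/160) = 0.795, above 0.79. With 135/160 = 84.4% it is 0.787, below 0.79. The 85% pass mark reproduces, and it allows 160 − 136 = 24 failed implants. The stated 85% effectiveness power also reproduces: with n = 160 × 0.9 = 144, the exact power of the confidence-interval rule at 58.8% against 46.3% is 85.2%. Nothing below changes it.

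**Step 1: no failed implant has an observed endpoint (q = 0).** The printed rate is 58.8% whatever *f* is. With failures counted it is 58.8% × (1 − *f*), so the gap is 58.8% × *f*.

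| Failed implants *f* | Printed | Failures counted | Gap (points) |
|---|---|---|---|
| 0% | 58.8% | 58.8% | 0 |
| 5% | 58.8% | 55.9% | 2.9 |
| 10% | 58.8% | 52.9% | 5.9 |
| 15% (pass mark) | 58.8% | 50.0% | 8.8 |
| 21% (at the 79% goal) | 58.8% | 46.5% | 12.3 |

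In counts at 15%: 80/136 = 58.8% against 80/160 = 50.0%.

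**Step 2: some failed implants are observed failures.** Printed rate = 58.8% × (1 − *f*) / [(1 − *f*) + *f* × *q*]. At *f* = 15%:
- *q* = 0 gives 58.8%.
- *q* = 0.5 gives 0.4998/0.925 = 54.0%.
- *q* = 1 gives 50.0%, with no overstatement.

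**Step 3: failed implants imaged after another treatment and credited.** For illustration, suppose all of them are imaged and are graded complete at the literature rate of 46.3%. At *f* = 15% the printed rate is 0.588 × 0.85 + 0.463 × 0.15 = 56.9%, against 50.0%. The gap is 6.9 points.

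**Step 4: one location.** Assume 40 subjects in a territory, 6 failed implants, and 20 of the 34 implanted subjects occluded. The row prints 20/34 = 58.8%; with failures counted it is 20/40 = 50.0%. A territory with no failed implants and the same occlusion rate would print the same 58.8%.

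**The case against.** The strongest reply is that retreatment already captures these subjects. Section 10.3.4 treats the effectiveness endpoint as missing only when two conditions hold together: "If the 1 year imaging is not available and if the subject did not experience a retreatment then the subject will be imputed". A retreated subject without an image is therefore an observed failure. The safety part of the same section uses the word for failed implants: "Any safety events which occur due to attempted implant or from retreatment". If treatment by another technique after a failed attempt is retreatment, those subjects stay in the denominator as failures and none can be credited as a success. This stands as a possible reading, but it is not settled. Section 7.11 describes retreatment for subjects who have received the device, and as something for which the subject returns. Another treatment in the same session fits neither description.

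Other points that stand:
- If implants rarely fail, the bias is negligible. The only rate in the documents is 34 of 34. That study covered basilar and carotid terminus aneurysms only, and the exact two-sided 95% upper limit for 0/34 failures is 1 − 0.025^(1/34) = 10.3%.
- Technical success counts failed implants directly on mITT, so overall failure is not hidden. Only its distribution by location is.
- The mITT rows also bring back subjects with major eligibility or DAPT deviations, so they are not simply PP under another name.
- With about 40 subjects per location (an assumed even split), the 95% half-width at 58.8% is about 15 points, wider than any gap at a passing technical-success rate. That limits what a row can show, but it does not excuse a bias in one direction.
- Section 10 leaves finer derivations to a separate SAP, which may contain a rule that is not visible in the text reviewed.

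The analysis in 10.3.10 that counts missing endpoints as failures is not a clear remedy. It reworks the primary analyses, and the effectiveness one is on PP, which contains no failed implants.

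**Conclusion.** The point holds as a correctable weakness in a descriptive analysis. Followed as written, 10.3.11 can give mITT occlusion rates that are too high by location, by sex and in the other subgroups. If no failed implant has an observed endpoint and implanted subjects reach 58.8%, the overstatement is 0 to 8.8 points for failed-implant shares of 0% to 15%. The 12.3-point case requires technical success at its 79% goal, which would fail the plan's own test. The overstatement falls to 0 if every failed implant is recorded as a retreatment failure.

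A reader might infer more: that all failed implants necessarily drop out, that overstatement is certain, or that the study's success claim is inflated. The documents do not support this. The DSA is not required but also not ruled out, retreatment may already capture some or all of these subjects, and the one observed implant rate implies no bias. The primary effectiveness decision rests on PP, which excludes failed implants by definition, so this display does not touch it.

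**What to change.** In 10.3.11 and the SAP:
1. Score every mITT subject without a successful PulseRider implant as a failure on the primary effectiveness endpoint, whatever imaging exists.
2. Apply the observed-data-only rule to implanted subjects alone.
3. State, for analysis purposes, whether alternative treatment after a failed attempt counts as retreatment, so that 7.11 and 10.3.4 agree.

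The cost is a few sentences. No extra imaging or subjects are needed, and the DSA exemption can stay. The mITT subgroup rates become somewhat less favourable wherever implants fail.
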